Official Title: Three-Dimensional Computed Tomography Assessment of Arcuate Foramen Variants and Their Surgical Implications: A Retrospective Observational Study

NCT Number: [To be assigned after registration]

Document Date: August 11, 2025

1. Background and Rationale

The arcuate foramen (AF) is an anatomical variation of the atlas (C1 vertebra) resulting from ossification of the posterior atlanto-occipital membrane, forming a bony bridge over the vertebral artery groove. While frequently asymptomatic, AF has been associated with vertebrobasilar insufficiency, cervicogenic headache, and neck pain. Importantly, AF may increase the risk of vertebral artery or suboccipital nerve injury during craniocervical junction surgery. This study aims to determine the prevalence and types of AF in a Turkish population using high-resolution three-dimensional computed tomography (3D CT) and to evaluate its potential surgical implications.

2. Objectives

Primary Objective: To determine the prevalence of complete and incomplete AF variants using 3D CT.

Secondary Objectives: (1) To assess the association between AF presence and demographic variables; (2) To evaluate interobserver agreement in AF detection.

3. Study Design

This is a retrospective, cross-sectional observational study conducted at Giresun University Faculty of Medicine. The study population includes adult patients who underwent head CT or CTA between January 2023 and July 2025.

4. Methods

Inclusion Criteria: Age \geq 18 years; high-quality CT or CTA images including atlas vertebra; complete demographic data. **Exclusion Criteria:** Significant motion or metallic artifact; prior cervical surgery or trauma; congenital anomalies obscuring anatomy. **Imaging Technique:** All scans were acquired using FUJIFILM SUPRIA CT system and reconstructed using OsiriX MD software with a 3D volume rendering technique. **AF Classification:** Complete (full bony ring) or incomplete (partial bony projection), further categorized by side (right, left, bilateral).

5. Outcome Measures

Primary Outcome: Prevalence of complete and incomplete AF with 95% confidence intervals.

Secondary Outcomes: Association between AF and age/sex; interobserver agreement measured by Cohen's Kappa.

6. Statistical Analysis Plan

Descriptive statistics will summarize continuous variables as mean \pm standard deviation and categorical variables as frequencies and percentages. Chi-square or Fisher's exact test will be used for categorical comparisons, and independent t-test for continuous variables. Interobserver agreement will be calculated using Cohen's Kappa. A p-value < 0.05 will be considered statistically significant. Post-hoc power analysis indicated a study power of 83% with 200 participants for an expected prevalence of 15% ($\alpha = 0.05$).

7. Ethics and Regulatory Compliance

The study protocol was approved by the Giresun University Faculty of Medicine Ethics Committee (Approval No: E-53593568-771-250207806, Date: July 31, 2024). All data were de-identified prior to analysis in compliance with relevant data protection regulations.

8. References

3. Arslan D, Özer MA, Govsa F, Kiti Ö. World Neurosurg. 2018;113:e579–e585.
5. Keser N, Çakla U, Özaydin B, et al. Istanbul Med J. 2019;20(5):377-381.

Study Protocol and Statistical Analysis Plan - Summary

Study Protocol

Official Title: Three-Dimensional Computed Tomography Assessment of Arcuate Foramen Variants and Their Surgical Implications: A Retrospective Observational Study

Background and Rationale: The arcuate foramen (AF) is an anatomical variation of the atlas (C1 vertebra) resulting from ossification of the posterior atlanto-occipital membrane, forming a bony bridge over the vertebral artery groove. While often asymptomatic, AF has been associated with vertebrobasilar insufficiency, cervicogenic headache, and neck pain. Importantly, AF may increase the risk of vertebral artery and suboccipital nerve injury during cranivertebral junction surgery.

Objectives: Primary Objective: To determine the prevalence of complete and incomplete AF variants using 3D CT. Secondary Objectives: (1) To assess the association between AF presence and demographic factors; (2) To evaluate interobserver agreement in AF detection.

Study Design: Retrospective, cross-sectional observational study conducted at Giresun University Faculty of Medicine. Data were collected from January 2023 to July 2025.

Methods: Inclusion criteria: Age \geq 18 years; high-quality CT or CTA images including the atlas; complete demographic data. Exclusion criteria: Motion or metallic artifact; prior cervical surgery or trauma; congenital anomalies obscuring anatomy. Imaging was performed on a FUJIFILM SUPRIA CT system and reconstructed using OsiriX MD with 3D volume rendering. AF was classified as complete (full bony ring) or incomplete (partial bony projection) and categorized by side (right, left, bilateral).

Outcome Measures: Primary: Prevalence of complete and incomplete AF (95% CI). Secondary: Association with age/sex; interobserver agreement (Cohen's Kappa).

Statistical Analysis Plan

Descriptive statistics: Continuous variables as mean \pm standard deviation; categorical variables as frequencies and percentages. Chi-square or Fisher's exact test for categorical data; independent t-test for continuous data. Interobserver agreement assessed by Cohen's Kappa. Significance level set at $p < 0.05$. Post-hoc power analysis indicated 83% power with 200 participants for an expected prevalence of 15% ($\alpha = 0.05$).

Ethics Approval: Approved by the Giresun University Faculty of Medicine Ethics Committee (Approval No: E-53593568-771-250207806, Date: July 31, 2024). All data were de-identified before analysis.

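### Does the plan need a surgical outcome, or a side-specific one, because its title and aim mention surgical implications?

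*Combined protocol and SAP*

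**What the plan says.** The official title, at the head of the document and again in the Summary, is an "Assessment of Arcuate Foramen Variants and Their Surgical Implications". The closing sentence of Section 1 gives two aims: to find the prevalence and types of arcuate foramen (AF) in a Turkish population, "and to evaluate its potential surgical implications". The background in the Summary mentions surgical risk but does not repeat that aim.

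Section 2 has one primary objective (prevalence of the two types) and two secondary ones (association with demographic variables; interobserver agreement). Section 5 matches them: "Primary Outcome: Prevalence of complete and incomplete AF with 95% confidence intervals", and then "Association between AF and age/sex; interobserver agreement measured by Cohen's Kappa".

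Section 4 classifies AF as "Complete (full bony ring) or incomplete (partial bony projection), further categorized by side (right, left, bilateral"). Section 6 names no variable for description; its general rule is to report "categorical variables as frequencies and percentages". The Summary repeats the classification, the outcomes and this rule.

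**The concern.** To evaluate something is normally to produce a result about it. Here the title and the stated aim promise an evaluation of surgical implications, yet no surgical variable is collected, compared or estimated. A reader could take the title as announcing a finding that the study cannot supply.

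Side makes the gap look avoidable. It is recorded for every case and is arguably what a surgeon would ask about first, although the documents do not say so. Yet it is in no objective or outcome and has no planned confidence interval.

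The classification also does not say where a patient with a complete ring on one side and a partial projection on the other belongs. That could touch the primary outcome, which is the prevalence of each type.

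**Working it through.** **1. Tracing the surgical aim.** Surgical implications appear in the title (twice) and in the Section 1 aim. They appear in 0 of 3 objectives, 0 of 3 outcomes and none of the Section 6 analyses. Removing the phrase would therefore alter no estimate, test or interval.

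**2. Tracing side.** Side is named in 0 of 3 outcomes. But Section 4 makes it a subdivision of type, type is the primary outcome, and the general rule in Section 6 covers it as a categorical variable. Counts by side are within the plan; only an explicit mention and an interval are absent.

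**3. The plan's own design figure.** Section 6 states: "Post-hoc power analysis indicated a study power of 83% with 200 participants for an expected prevalence of 15" per cent, with α = 0.05. It gives no null value, comparator or sidedness, so the 83% cannot be reproduced. The one-sample normal approximation is

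power = Φ{[|p₁ − p₀|√n − z√(p₀(1 − p₀))] / √(p₁(1 − p₁))}, with n = 200, p₁ = 0.15, z = 1.96.

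- p₀ = 0.085 (assumed): power 0.85.
- p₀ = 0.09 (assumed): power 0.79.

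So 83% is reachable with a suitable null between these, but the documents neither confirm nor refute it. The present point does not depend on it; only the 200 and the 15% are used below.

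**4. What intervals by side would add.** Assume that 15% means any AF, counted per patient (the plan does not say).

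- Patients with AF: 200 × 0.15 = 30; exact 95% CI for 30/200 is 10.4% to 20.7%.
- Type-by-side cells: 2 × 3 = 6. An even spread (assumed) gives 30/6 = 5 per cell.
- 5/200 = 2.5%; exact 95% CI 0.8% to 5.7%.

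Such an interval describes and no more, and a reader can compute it from the count and the denominator.

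**5. Per patient or per side.** Pooling the 30 patients over 400 sides, with bilateral share b (not in the documents), gives 30(1 + b)/400: 7.5% at b = 0 and 15.0% at b = 1. This averages the two sides and says nothing firm about either. If all 30 were left-only, the right side would have 0/200 against 15% per patient. The plan uses no per-side denominator, and the right, left and bilateral counts themselves show b. The range therefore identifies no error.

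**6. Different types on the two sides.** Each such patient is 1/200 = 0.5 percentage points in the prevalence of complete or incomplete AF. The prevalence of any AF does not move, since the patient counts once under every rule. For scale, if the 30 cases split evenly by type (assumed), each type has 15/200 = 7.5%, with an approximate 95% half-width of 1.96 × √(0.075 × 0.925/200) = 3.65 points. With k such patients the shift is 0.5k points; k is not in the documents.

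**The case for a change.** The strongest case for acting is the counting rule. The primary outcome is the prevalence of each type, the categories do not place a patient with different types on the two sides, and a written rule would cost one line. It is true that the rule is missing and that the choice moves the two figures. But it is separate from the question of surgical scope. Listing such patients in their own row of a side table would not settle whether they count as complete, incomplete or both in the primary prevalence. Analysts must choose when they tabulate, and a table by type and side that shows these patients lets a reader recount under any rule.

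The second argument is that the word evaluate promises a result, and that aligning the wording is almost free. As an editorial remark this stands: one sentence saying that surgical relevance is discussed from the prevalence results and prior literature would help a reader. But the aim speaks of potential implications, the surgical rationale sits in the background, and Sections 2 and 5 are clear about what is estimated.

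Adding side to the outcome lists also has a drawback. The document is dated August 11, 2025, after the imaging window closed in July 2025, and it already reports a post-hoc power analysis. A new outcome entered at that point might itself be post hoc and would need to be disclosed as such. Reporting side under the existing descriptive rule avoids that.

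**Conclusion.** The textual observation is correct: surgical implications are in the title and the Section 1 aim and nowhere in the objectives, outcomes or analyses, and side is in no outcome. Its effect on the planned estimates, tests and intervals is nil. The surgical phrase is loose wording about interpretation. Side is covered by the classification and the general descriptive rule, and at roughly 5 patients per cell an interval would change no conclusion. The rule for patients with different types on the two sides is a small gap that analysts can fill and report, worth 0.5 percentage points per patient, with the total unknown.

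This rests on 200 analysed participants, on reading the 15% as any AF per patient, and, for the cell and half-width figures, on even splits. The finding that no planned analysis depends on the surgical phrase needs none of these assumptions. No change to the plan is called for.

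### The stated target is a Turkish population but the sample is adults scanned for clinical reasons at one hospital; any enrichment for AF-linked complaints would raise the prevalence by an unknown amount that the 95% CI does not show

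*Combined protocol and SAP*

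**What the plan says.** The target is in Section 1 (Background and Rationale): "This study aims to determine the prevalence and types of AF in a Turkish population". The source of the sample is in Section 3 (Study Design), at a single university hospital: "The study population includes adult patients who underwent head CT or CTA between January 2023 and July 2025".

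Section 1 also says that "AF has been associated with vertebrobasilar insufficiency, cervicogenic headache, and neck pain". The same sentence notes that the variant often causes no symptoms.

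Inclusion under Section 4 (Methods) rests on adult age and "high-quality CT or CTA images including atlas vertebra; complete demographic data". The exclusions are "Significant motion or metallic artifact; prior cervical surgery or trauma; congenital anomalies obscuring anatomy". The Summary's Methods paragraph has essentially the same criteria. None of them concerns why the scan was ordered.

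Section 5 gives "Primary Outcome: Prevalence of complete and incomplete AF with 95% confidence intervals" and "Secondary Outcomes: Association between AF and age/sex; interobserver agreement measured by Cohen's Kappa". Neither Section 6 nor the Summary records the scan indication, separates head CT from CTA, plans a sensitivity analysis for selection, or limits the conclusion to referred patients. The Summary does not repeat the population aim.

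**The concern.** The primary result is a count of how common a variant is, so who gets into the sample matters more than any test. Patients enter because a clinician ordered a head CT or CTA. Section 1 associates the variant with complaints that could plausibly be behind some of those orders. If so, entry is not independent of the condition being counted, and carriers would be over-represented relative to the population named in Section 1.

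This is separate from how the 200 participants are chosen among eligible scans. Including every eligible scan would leave the enrichment in place, and a larger sample would only narrow the interval around a shifted value. The 95% CI is the only measure of uncertainty planned for the primary outcome, and a binomial interval does not reflect selection. A reader of the final report would see, say, 15% with an interval and the words of Section 1, with no means of judging how far the referral pattern contributed.

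**Working it through.** **Figures from the plan.** 200 participants and an expected prevalence of 15% (Section 6 and Summary). The stated 83% power cannot be reproduced because no comparator is given. In a two-sided one-sample test it would need a null of roughly 8.7% or 23.3%. Nothing below depends on it.

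**What the interval covers.** Half-width at 15% of 200: 1.96 × √(0.15 × 0.85 / 200) = 4.9 points. The plan names no interval method. For 30/200 the Wald interval is 10.1% to 19.9% and the Wilson interval 10.7% to 20.6%.

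**Enrichment model.** Let *a* and *b* be AF prevalence without and with the complaints, linked by an odds ratio OR, so that *b* = OR·*a* / (1 − *a* + OR·*a*). Let s0 be the share with complaints in the population and s1 the share in the sample.

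- Population prevalence = (1 − s0)·*a* + s0·*b*
- Sample prevalence = (1 − s1)·*a* + s1·*b*
- Bias = (s1 − s0) × (*b* − *a*)

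The documents give none of OR, s0 or s1. Assumed here: s0 = 10%, s1 = 30% to 70%, OR = 1.5 to 3.

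**Population prevalence fixed at 15%.** Solving 0.9*a* + 0.1*b* = 0.15 gives (*a*, *b*) of 14.4% and 20.2% at OR 1.5, 13.9% and 24.5% at OR 2, and 13.2% and 31.3% at OR 3. Expected sample prevalence, with the bias in points and the coverage of the true 15% by a nominal 95% Wilson interval:

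| OR | s1 = 30% | s1 = 50% | s1 = 70% |
|---|---|---|---|
| 1.5 | 16.2% (+1.2; 90.5%) | 17.3% (+2.3; 81.8%) | 18.5% (+3.5; 68.6%) |
| 2 | 17.1% (+2.1; 83.7%) | 19.2% (+4.2; 58.3%) | 21.3% (+6.3; 29.8%) |
| 3 | 18.6% (+3.6; 66.4%) | 22.2% (+7.2; 19.9%) | 25.9% (+10.9; 2.2%) |

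With OR = 1, or with s1 = s0, the bias is zero and coverage is 94.1%.

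**15% placed instead in patients without the complaints.** Odds are 0.15/0.85 = 0.1765, so *b* is 20.9%, 26.1% and 34.6% at OR 1.5, 2 and 3.

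- OR 1.5, s1 = 30%: bias = 0.2 × (20.9 − 15.0) = 1.2 points
- OR 2, s1 = 50%: bias = 0.4 × (26.1 − 15.0) = 4.4 points
- OR 3, s1 = 70%: bias = 0.6 × (34.6 − 15.0) = 11.8 points

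The two anchorings agree closely: about 1 to 12 points overall, and about 4 at OR 2 with a 50% share.

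**Would patients with other indications give the population figure?** Not exactly. A population includes people with these complaints. At OR 2 under the second anchoring it is 0.9 × 15.0% + 0.1 × 26.1% = 16.1%, while the other-indication stratum shows 15.0%. Under the first anchoring the pair is 15.0% and 13.9%. In both the stratum is about 1 point low. With 100 patients its half-width at 15% is 1.96 × √(0.15 × 0.85 / 100) = 7.0 points.

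**The case against.** The mechanism is inferred. Section 1 gives an association of no stated size and says that AF is often silent. No section says that these complaints lead to head CT or CTA, and the inference is weaker for neck pain than for vertebrobasilar symptoms. Nothing in the documents shows that half the sample, or any given share, was scanned for such reasons. Hospital imaging series share this limitation in general, no binomial interval covers selection, and Section 3 is open about where patients come from. All of this stands. It limits the claim to a possible bias of unknown size, but it does not remove the mismatch between the population named in Section 1 and the sample in Section 3.

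Four stronger readings are tempting and are not supported:

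- A reader might infer that the prevalence will be too high. No indications are given, so this cannot be said.
- A reader might infer that the bias at OR 2 and a 50% share exceeds the CI half-width, by comparing the pooled 20.5% with the 15% in patients without complaints (5.5 points against 4.9). That benchmark leaves out people in the population who have the complaints. Against the population the bias is 4.2 to 4.4 points.
- A reader might infer that the other-indication stratum is the right population estimate. It is itself slightly low, as shown above.
- A reader might infer that comparison with other series is impossible, or that the age and sex associations are distorted. The former depends on studies not available here. The latter needs a link between indication and age or sex that the documents do not give.

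The cost objection also has force. The data are described as already collected and de-identified (Summary, Study Design; Section 7), so indication may be harder to recover than two extra fields suggest.

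**Conclusion.** The point holds in a limited form. The plan names a target that its sample does not directly represent, supplies a reason in Section 1 why the two could differ, and provides nothing to detect or describe the difference. The direction would be upward if AF-linked complaints are more common among scanned patients than in the population. The calculated size rests wholly on the assumed odds ratios and shares, and zero is possible. Within the range examined the bias can be small beside the sampling error or well above it. The point affects what the study can conclude about a population. It does not invalidate the prevalence as a description of adults scanned at this centre.

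**What to change.** In Sections 1, 3, 5 and 6 and the Summary, state the target of the primary estimate as adults undergoing head CT or CTA at this centre, and remove the unqualified population claim from Section 1. This part needs no data.

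In Sections 4 to 6 and the Summary, add two variables:

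- scan type (head CT or CTA);
- indication, where existing requests allow: vertebrobasilar symptoms, cervicogenic headache or neck pain; other; unknown. Headache should count as AF-linked only as far as Section 1 supports, which is the cervicogenic form.

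Report complete and incomplete AF prevalence with 95% CI overall and, as a sensitivity analysis, by indication group and by scan type. Present the other-indication group as a check on enrichment and a likely slightly low figure, not as the population estimate.

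The cost is two fields and one table, with no new scans or readings. Stratum intervals would be about 7 points either side at 100 patients. About 30 AF cases are expected (15% of 200), so cells split by complete or incomplete form and by stratum will be small and should be read descriptively. Some indications will be missing, and extraction may mean going back to source records. If indication cannot be recovered, the change of target and the split by scan type still stand.

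### Does one word missing from the Summary's artifact exclusion, with no stated scan-selection rule, leave the prevalence denominator undefined?

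*Combined protocol and SAP*

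**What the plan says.** The primary outcome in Section 5 is "Prevalence of complete and incomplete AF with 95% confidence intervals". These passages bear on which scans are counted:

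- **Artifact, Section 4:** "Significant motion or metallic artifact; prior cervical surgery or trauma; congenital anomalies obscuring anatomy". The first word is not defined.
- **Artifact, Summary (Methods):** "Exclusion criteria: Motion or metallic artifact; prior cervical surgery or trauma; congenital anomalies obscuring anatomy". The list is the same apart from that word.
- **Image quality:** both texts also admit only high-quality CT or CTA that shows the atlas. High-quality is not defined either.
- **Source and window, Section 3:** "The study population includes adult patients who underwent head CT or CTA between January 2023 and July 2025", at one university faculty.
- **Window, Summary (Study Design):** "Data were collected from January 2023 to July 2025".
- **Ethics approval, Section 7:** "Date: July 31, 2024". The document itself is dated August 11, 2025.
- **Aim, Section 1:** "This study aims to determine the prevalence and types of AF in a Turkish population using high-resolution three-dimensional computed tomography".
- **Size, Section 6:** "a study power of 83% with 200 participants for an expected prevalence of 15" per cent.

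No section says whether all eligible scans, consecutive scans or a sample were taken, or gives counts screened and excluded.

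**The concern.** A prevalence is only as clear as its denominator. Read literally, the two artifact lists differ: a scan with slight motion artifact survives Section 4 and fails the Summary. Artifact could also affect whether a small bony projection is seen, so the exclusion is not obviously unrelated to the outcome. Two people applying the two lists to one archive could report different prevalences and intervals, and the 95% CI does not cover uncertainty about who was counted.

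The silence on sampling adds to this. If the 200 are a selection from a larger eligible pool, the reader cannot tell how they were chosen. Two further features seem to point the same way. Part of the scan window falls after the ethics approval, so the scan list could not have been complete at approval. The aim also speaks of a Turkish population, although the source is one hospital's imaged adults.

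**Working it through.** **The plan's own figure.** The 83% power can be neither reproduced nor refuted, because no comparison prevalence is given. With a one-sample test (normal approximation, n = 200, true value 15%, two-sided 0.05), 83% requires a null of about 8.7% or 23.3%. Nothing below depends on it. The inputs used are n = 200 and 15% from Section 6, that is 0.15 × 200 = 30 AF-positive.

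**Precision.** Half-width = 1.96 × √(0.15 × 0.85 / n).

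- n = 200: 4.95 points
- n = 190: 5.08 points
- n = 180: 5.22 points
- n = 160: 5.53 points

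**Effect of one scan.** Dropping one AF-positive scan gives 29/199 = 14.57% (-0.43 points). Dropping one AF-negative scan gives 30/199 = 15.08% (+0.08 points).

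**Effect of the wording.** The documents give no artifact counts, so what follows is an assumed range. Let the broader (Section 4) set have prevalence 15%, let a be the share with lesser artifact, and let r be how often AF is read in those scans relative to the rest. If p is the prevalence in the other scans, then 0.15 = (1 - a)p + a·r·p. The stricter (Summary) set therefore gives p = 0.15 / (1 - a + a·r).

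| a | r = 0.5 | r = 1 | r = 1.5 |
|---|---|---|---|
| 5% | 15.38% | 15.00% | 14.63% |
| 10% | 15.79% | 15.00% | 14.29% |
| 20% | 16.67% | 15.00% | 13.64% |

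The shift runs from -1.36 to +1.67 points. The larger is 1.67 / 4.95, about one third of the half-width.

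**A harsher check.** Now put 15% in the clean scans and let the others, a share f of the broader set, have AF read at rate q. Pooled prevalence = (1 - f) × 0.15 + f × q. With f = 20%, q = 0 gives 12.0% and q = 30% gives 18.0%, a shift of 3 points either way. With q = 0 the shift is 15f points, so reaching 4.95 needs f = 4.95 / 15 = 33%. About a third of the scans would need lesser artifact, with no AF seen in any of them, although all had passed as high-quality.

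**The two lists side by side.** The Summary repeats Section 4's three exclusions in the same order and loses one adjective. It compresses the rest of the protocol in the same way. That pattern fits condensation better than a second, stricter rule.

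**Dates.** January 2023 to July 2025 is 12 + 12 + 7 = 31 months, of which 12 (August 2024 to July 2025) follow the approval date. This does not bear on the denominator, since a date window plus eligibility criteria can define a set before all its members exist. Section 3 states plainly that these are scan dates. The Summary's sentence can be read as data from that period.

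**Target population.** Section 1 uses the indefinite article and describes the aim, while Section 3 gives the operative source. This is a matter of generalisability and does not alter which scans are counted.

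**The case for a change.** The strongest case for a change is that both lists are current text, both are presented as the exclusion criteria, and aligning them would cost one word. The high-quality requirement is itself undefined, so it cannot formally reconcile them. Section 3 may imply that all eligible patients were taken, but it does not say so. Classification by side also needs both sides to be readable, and the plan does not say whether one unreadable side excludes a scan.

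All of that is accurate as description. Comparing the shift with the half-width also shows scale only: an interval does not absorb a systematic difference. The calculation covers the artifact wording alone, and the documents give no basis for sizing the effect of an unstated sampling route.

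What does not follow is a defect in the planned analysis. The document postdates the scan window, so one screening practice has probably been applied already, and the remedy would mostly record it. Estimating prevalence with and without the lesser-artifact scans would go further. It needs an artifact flag for each scan, perhaps a second look at every included scan, for an effect that is small under every assumption tried. Nothing in the documents suggests that scans were chosen with knowledge of AF status.

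**Conclusion.** The concern does not call for a change to the plan. The difference between the artifact lists is probably clerical, and the silence on selection is missing detail that a competent study report fills by naming the rule used and giving counts screened, excluded by reason and included. The approval date and the Turkish-population wording do not bear on the denominator.

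Under the assumed 5% to 20% share of lesser-artifact scans and a reading ratio of 0.5 to 1.5, the choice of wording moves a 15% prevalence by -1.4 to +1.7 points, and by nothing if AF is read equally often. The half-width at n = 200 is 4.95 points. No direction of bias can be shown, and the estimator and its interval are the same under either reading.

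The conclusion rests on two assumptions: that one artifact rule was applied throughout, and that scans were not selected on anything related to AF. Evidence against the second would reopen the question.

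### Does the classification leave complete and incomplete prevalence undefined for a patient with a different type on each side?

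*Combined protocol and SAP*

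**What the plan says.** Section 4 (AF Classification) uses two types and three side codes: "Complete (full bony ring) or incomplete (partial bony projection), further categorized by side (right, left, bilateral"). The Methods paragraph of the closing summary repeats the scheme and adds no rule: "AF was classified as complete (full bony ring) or incomplete (partial bony projection) and categorized by side (right, left, bilateral"). The objective in Section 2 is "To determine the prevalence of complete and incomplete AF variants using 3D CT", and the outcome in Section 5 is "Prevalence of complete and incomplete AF with 95% confidence intervals".

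The unit of analysis is not stated outright, but the wording points to patients. Section 3 says "The study population includes adult patients who underwent head CT or CTA between January 2023 and July 2025", and the power statement in Section 6 counts 200 participants. Section 6 summarises "categorical variables as frequencies and percentages" and names no interval method. The two secondary objectives in Section 2 concern whether AF is present and how well observers agree in detecting it. Neither concerns its type.

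**The concern.** AF is a finding on one side of the atlas, so each side can have its own type. The scheme names type first and side second, as if both sides of a bilateral case always matched. Read as six patient-level cells (two types by right, left, bilateral), it has none for a patient who is complete on one side and incomplete on the other.

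Such a patient could be placed wholly in either type, counted in both, or left out of both. The first choice moves one subtype prevalence up and the other down. Counting in both makes the subtypes add to more than any-AF prevalence, and leaving out makes them add to less. The data are retrospective, so the choice could be made after the counts are known. A further worry is that an analyst might switch to sides, 400 in place of 200, and treat them as independent. These are the primary figures, so the question deserves a check.

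**Working it through.** **The plan's own figure.** Section 6 gives 83% power for 200 participants at an expected prevalence of 15%, alpha 0.05. It states no null value or comparison, so the figure can be neither confirmed nor refuted. It is matched only by choosing an effect, for example a 15% null against 22%, one-sided (83.4%). Nothing below depends on it. Only N = 200 and 15% are used: 0.15 × 200 = 30 AF patients.

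**Mixed patients.** Their number, m, is not in the documents, so a range is assumed. If c is the number of patients with complete AF only, complete prevalence is c/200 when mixed patients are excluded from that type and (c + m)/200 when they are included. The shift is m/200. The two subtypes sum to 30/200 if each mixed patient goes to one type, (30 + m)/200 if counted in both, and (30 − m)/200 if counted in neither. The complete-only and incomplete-only counts are also assumed.

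| m | complete only / incomplete only | complete prevalence, mixed excluded or included | Wilson 95% CI at the lower value | sum: one type / both / neither |
|---|---|---|---|---|
| 0 | 15 / 15 | 7.5% | 4.6–12.0% | 15 / 15 / 15% |
| 2 | 14 / 14 | 7.0% or 8.0% | 4.2–11.4% | 15 / 16 / 14% |
| 4 | 10 / 16 | 5.0% or 7.0% | 2.7–9.0% | 15 / 17 / 13% |
| 6 | 12 / 12 | 6.0% or 9.0% | 3.5–10.2% | 15 / 18 / 12% |
| 9 | 10 / 11 | 5.0% or 9.5% | 2.7–9.0% | 15 / 19.5 / 10.5% |

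Up to 6 mixed patients among 30, the shift stays within sampling error. At 9 it does not: 9.5% lies above the upper limit of 9.0%. Any-AF prevalence is 30/200 = 15.0% in every row (Wilson 95% CI 10.7–20.6%).

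**Tests and kappa.** For presence or detection, a mixed patient is simply positive. The chi-square or Fisher comparison by sex, the t-test on age and the kappa for detection therefore do not depend on how type is allocated. The plan specifies no test or kappa on type.

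**Sides as the unit.** Assume 12 of the 30 are bilateral.
- Side prevalence = (30 + 12)/400 = 0.105.
- Between-side correlation = (12/200 − 0.105²)/(0.105 × 0.895) = 0.521.
- SE ratio = √1.521 = 1.233.
- Size of a nominal 5% test against a patient-level factor = 2[1 − Φ(1.96/1.233)] = 11.2%. With 6 or 18 bilateral patients it is 8.2% or 13.5%.
- For right against left, the same correlation makes the naive test conservative: √(1 − 0.521) = 0.692, 1.96/0.692 = 2.83, size about 0.5%.

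The arithmetic is sound, but it describes an analysis the plan does not propose. The correlation is also for any AF, so it does not give the error in the interval for either subtype.

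**The case for a change.** The strongest case for a change is that the split by type is the primary objective, the bilateral code shows that two-sided disease was foreseen, and a few words would settle unit, denominator and mixed cases before anyone counts. No other text in the document supplies the rule. Without it, the choice can be made after the data are seen, and with enough mixed patients it would be visible in the primary figures, as the last row of the table shows.

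Part of this stands: the rule, the unit and the denominator are unwritten, and writing them down would be tidier. Three steps beyond that do not follow. First, the scheme does not shut the mixed patient out. Complete-right together with incomplete-left is an ordinary entry once each side has been read, and the side codes require that reading. Under that entry the two prevalences overlap, which is legitimate. Second, the damage to chi-square tests and kappa presupposes analyses of type that the objectives do not contain, and the inflated error presupposes 400 independent sides where the plan counts patients. Third, poor coverage of simple Wald intervals in sparse cells (80% at a prevalence of 1.5%, 91% at 2%, n = 200) cannot be charged to a plan that names no interval method.

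**Conclusion.** No change to the plan follows. What remains is a missing detail that an analyst fills sensibly: patients as the denominator, type recorded for each side, and mixed patients shown so that complete only, incomplete only and mixed add to any AF. The data this needs are those the right, left and bilateral codes already call for.

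The effect is confined to the two subtype prevalences and equals m/200, where m is the unknown number of mixed patients: zero for none, 2 points for an assumed 4, and 4.5 points for an assumed 9. Any-AF prevalence, its association with age and sex, and detection agreement do not move. The conclusion rests on reading presence and detection as patient-level yes/no outcomes and on patients being the unit, as the population and sample-size wording indicate. It would need another look if the report tested type against demographics, computed kappa on type, or treated sides as independent.
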